## 1. List of Abbreviations

Acronym	Definition
ADE	Adverse Device Event
AE	Adverse Event
ASES	American Shoulder and Elbow Surgeons
CI	Confidence Interval
CIP	Clinical Investigation Plan
CRF	Case Report Form
eCRF	Electronic Case Report Form
EDC	Electronic Data Capture
HA	Hemi-Shoulder Arthroplasty
ICF	Informed Consent Form
IFU	Instructions for Use
IRB	Institutional Review Board
ITT	Intent-to-Treat
LTFU	Lost to Follow-Up
ORIF	Open Reduction Internal Fixation
PP	Per Protocol
RFX	Reversible Fracture
RSA	Reverse Shoulder Arthroplasty
SADE	Serious Adverse Device Effect
SAE	Serious Adverse Event
SAP	Statistical Analysis Plan
TSA	Total Shoulder Arthroplasty
UADE	Unanticipated Adverse Device Effect

## 2. Synopsis

Study Title:	A Post-Market Clinical Evaluation of the ReUnion Reversible Fracture (RFX) System
Study Treatment:	ReUnion RFX System
Study Design:	

• Post-Market

• Multicenter

• Prospective

• Two arms

• Non-Randomized

Objectives	
The objective of this clinical investigation is to demonstrate the safety and efficacy/performance of the ReUnion RFX System.
 
Efficacy/performance of the procedure will be measured by the American Shoulder and Elbow Surgeons (ASES) Shoulder Score.
 
Safety of the ReUnion RFX System will be demonstrated through reporting of device-related intraoperative and postoperative Adverse Events (AEs).

Target Population	100 subjects are to be enrolled in this clinical investigation. Enrolled subjects will be assessed at Preoperative, Operative/Discharge, and at 6 Weeks, 6 Months, 12 Months, 24 Months and annually thereafter up to 10 years following the index procedure.
Endpoints	
Primary Endpoint – Arm A (Total Shoulder Arthroplasty / Hemiarthroplasty):
 
The objective of the clinical investigation is to demonstrate non-inferiority of the ASES Shoulder Score at 24 months postoperative compared to the benchmark literature for Arm A.
 
Primary Endpoint – Arm B (Reverse Shoulder Arthroplasty):
 
The objective of the clinical investigation is to demonstrate non-inferiority of the ASES Shoulder Score at 24 months postoperative compared to the benchmark literature for Arm B.
 
Secondary Endpoints (for both Arm A and B):
 
Information on the following outcomes will be assessed:
 
 
• Safety: Incidence of device-related intraoperative and postoperative AEs
 
• Efficacy/Performance: Implant survivorship will be monitored
 

Inclusion Criteria:	
 
a. Subject is willing to sign the informed consent.
 
b. Subject is willing and able to comply with postoperative scheduled clinical evaluations.
 
c. Subject is male or non-pregnant female and 18 years or older at the time of surgery.
 
d. When used with ReUnion Total Shoulder Arthroplasty (TSA) Humeral & Glenoid components as a Hemiarthroplasty or Total Shoulder Replacement, subject has one or more of the following: 
 
• Aseptic necrosis of humeral head
 
• Painful, disabling joint disease of the shoulder resulting from degenerative arthritis, rheumatoid arthritis or post-traumatic arthritis
 
• Proximal humeral fracture and/or dislocation
 
• Clinical management problems where arthrodesis or alternative reconstructive techniques are less likely to achieve satisfactory results
 
• Previous unsuccessful total shoulder replacement, resurfacing or other procedure
 
 
 
e. When used with ReUnion RSA Humeral & Glenoid Components as a primary, fracture or revision total shoulder replacement, subject's joint has gross rotator cuff deficiency, a functional deltoid muscle and is anatomically and structurally suited to receive the implant, and subject has one or more of the following: 
 
• Painful, disabling joint disease of the shoulder resulting from degenerative arthritis or rheumatoid arthritis
 
• Proximal humeral fracture
 
• Previously failed shoulder joint replacement
 
 
 

Exclusion Criteria:	

a. Subject has an active or suspected latent infection in or about the shoulder joint.

b. Subject has mental or neuromuscular disorder which would create an unacceptable risk of prosthesis instability, prosthesis fixation failure or complications in postoperative care.

c. Subject has bone stock compromised by disease, infection or prior implantation which cannot provide adequate support and/or fixation to the prosthesis.

d. Subject has anticipated activities which would impose high stresses on the prosthesis and its fixation.

e. Subject is obese such that he/she produces a load on the prosthesis which can lead to failure of fixation of the device or to failure of the device itself.

f. Subject has concomitant disease(s) which may significantly affect the clinical outcome.

g. For Total Shoulder Arthroplasty and Hemi-Shoulder Arthroplasty: Subject has absent, irreparable or non-functioning rotator cuff and other essential muscles.

---------------------	---

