#### 8.3. SECONDARY ENDPOINTS (FOR BOTH ARM A AND B)

In addition to the principal endpoint, information on the following outcomes will be assessed up to 10 years after the index procedure:

- Safety: Incidence of device-related intraoperative and postoperative AEs
- Efficacy/Performance: Implant survivorship will be monitored

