### 11.3.3. Secondary Endpoints

The incidence of device-related AEs and implant survivorship will be assessed up to ten years after the index procedure and monitored through collection and analyses. These analyses will be part of the annual and final reports.

Furthermore, time to (earliest) device-related AEs will be analyzed as well. For analysis of the time to the (earliest) device-related AEs as well as the time to secondary procedure (revision, removal, reoperation), the Kaplan-Meier method will be used. The time between surgery and the last available assessment will be used together with the time between date of surgery and the date of secondary procedure. Considered variables, the level of measurement and the planned analysis steps are listed in detail in the SAP.

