3.1. FRAMEWORK

All quantitative variables, including those based on calculations (secondary elements), will be analyzed with a case summary evaluation before the detailed characteristics and parameters can be evaluated. A case summary contains a listing of the number of valid cases/values, missing cases/values (if any) and total cases/values in the specific analysis. In general, as central position parameter for quantitative variables the mean, median and mode will be analyzed. As variation parameter the standard deviation, 95% confidence interval of the mean, interquartile range and range (based on maximum and minimum) will be calculated. All quantitative variables will be assessed for normality using the Shapiro-Wilk test. For optional visualization of quantitative variables, box-and-whisker plots will be used. Additional analyses like skewness and kurtosis measures or standard errors are also optional.

All qualitative variables, including those based on summaries (secondary elements), will be analyzed listing the proportions, frequencies, column and row totals, and missing proportion (if any).

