6.1. HARMS AND SAFETY

Categorization and definitions of (Serious-, Unanticipated-) Adverse Device Effects, (Serious-) Incidents are given in the CIP.

Evaluation Variable / Question	Level of Measurement	Analysis Plan	Inclusion		
Adverse Events / Incidents			IR	FR	N/A
Perioperative/Postoperative AE (Variable(s): PERPOST)	Qualitative, nominal	Proportions, frequencies, column and row totals, missing proportion (if any).	X	X	
Device-Related Adverse Event / Incident (Variable(s): AEEVENT; AEOTHER)	Qualitative, nominal	Proportions, frequencies, column and row totals, missing proportion (if any). Listing of other Events/Incidents.	X	X	
Describe the AE/Incident (Variable(s): AEDESCRP)	Qualitative, nominal	Listing of other Events/Incidents Description.			X
Unanticipated Adverse Device Event? (Variable(s): AEUADE)	Qualitative, nominal	Proportions, frequencies, column and row totals, missing proportion (if any).	X	X	
Severity (Variable(s): AESEVER)	Qualitative, nominal	Proportions, frequencies, column and row totals, missing proportion (if any).	X	X	
Action Taken (Variable(s): ACTNONE; ACTMEDS; ACTSURG; ACTSHORT;	Qualitative, nominal	Proportions, frequencies, column and row totals, missing proportion (if any).			X

ACTPROHS; ACTOTHER; ACTOTHSP)		Listing of given Other specifications.			
AE Resolution (Variable(s): AERESOLV)	Qualitative, nominal	Proportions, frequencies, column and row totals, missing proportion (if any).			X
Outcome (Variable(s): AEONWOTR; AEONWTTR; AEREWOTR; AEREWTTR; AETEDISB; AEPERMD; AESUEXP)	Qualitative, nominal	Proportions, frequencies, column and row totals, missing proportion (if any).			X
Creation of variable Number of Adverse Device Effects by Site (Variable(s): AEEVENT; SITENUM)	Qualitative, nominal	Proportions, frequencies, column and row totals, missing proportion (if any).	X	X	
Creation of variable Number of Adverse Device Effects per Subject and Site (Variable(s): AEEVENT; SITENUM; SUBID)	Qualitative, nominal	Proportions, frequencies, column and row totals, missing proportion (if any).	X	X	

Table 6.1.1: Adverse Events / Incidents Tables List

Evaluation Variable / Question	Level of Measurement	Analysis Plan	Inclusion		
			IR	FR	N/A
Reoperation					

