7.1. FREQUENCIES

All answered response options must be listed with the appropriate label, other response options do not have to be displayed necessarily. In the event of missing answers, the frequencies must be included in an extra row as well (“Missing”). All given answers must be added up in an extra row (“Total”). In addition to the number of frequencies, percentages must be displayed in a separate column. Each analysis arm must be displayed separately, as well as a overall result of both arms has to be created. The two arms and the overall results can be combined in one table or in three separate tables.

“Analysis Section” – “Variable Label” – Frequencies

Characteristic		ARM A		ARM B		Total	
		n	%	n	%	n	%
“Variable Label”	“Response A”	“xxx”	“xxx”	“xxx”	“xxx”	“xxx”	“xxx”
	“Response B”	“xxx”	“xxx”	“xxx”	“xxx”	“xxx”	“xxx”
	Missing	“xxx”	“xxx”	“xxx”	“xxx”	“xxx”	“xxx”
	Total	“xxx”	“xxx”	“xxx”	“xxx”	“xxx”	“xxx”

Table 7.1.1: Frequencies Table Template

If multiple subgroups/clusters (e.g. Sites, Visits) should be displayed in one table, an extra column (“Group X”) and/or extra rows (“Group Y”) must be added. Same applies to (sub-) questions, which can be merged in one table. It is recommended to add an extra “Total” column and row, for adding up the subgroups, if possible, from a statistical point of view. In addition, subgroups must be named in the headline as well (“by Group X and by Group Y”).

“Analysis Section” – “Variable Label” – Frequencies – by “Group X” and “Group Y”

Characteristic		“Group X1”						“Group X2”						Total	
		Arm A		Arm B		Total “G X1”		Arm A		Arm B		Total “G X2”			
		n	%	n	%	n	%	n	%	n	%	n	%		
“Group Y1”	“Response A”	“xxx”	“xxx”	“xxx”	“xxx”	“xxx”	“xxx”	“xxx”	“xxx”	“xxx”	“xxx”	“xxx”	“xxx”	“xxx”	“xxx”
	“Response B”	“xxx”	“xxx”	“xxx”	“xxx”	“xxx”	“xxx”	“xxx”	“xxx”	“xxx”	“xxx”	“xxx”	“xxx”	“xxx”	“xxx”
	Missing	“xxx”	“xxx”	“xxx”	“xxx”	“xxx”	“xxx”	“xxx”	“xxx”	“xxx”	“xxx”	“xxx”	“xxx”	“xxx”	“xxx”
	Total	“xxx”	“xxx”	“xxx”	“xxx”	“xxx”	“xxx”	“xxx”	“xxx”	“xxx”	“xxx”	“xxx”	“xxx”	“xxx”	“xxx”
“Group Y2”	“Response A”	“xxx”	“xxx”	“xxx”	“xxx”	“xxx”	“xxx”	“xxx”	“xxx”	“xxx”	“xxx”	“xxx”	“xxx”	“xxx”	“xxx”
	“Response B”	“xxx”	“xxx”	“xxx”	“xxx”	“xxx”	“xxx”	“xxx”	“xxx”	“xxx”	“xxx”	“xxx”	“xxx”	“xxx”	“xxx”
	Missing	“xxx”	“xxx”	“xxx”	“xxx”	“xxx”	“xxx”	“xxx”	“xxx”	“xxx”	“xxx”	“xxx”	“xxx”	“xxx”	“xxx”
	Total	“xxx”	“xxx”	“xxx”	“xxx”	“xxx”	“xxx”	“xxx”	“xxx”	“xxx”	“xxx”	“xxx”	“xxx”	“xxx”	“xxx”

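### Safety is to be demonstrated by reporting events, but the plan has no safety criterion and no confidence interval on any adverse-event proportion

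*Protocol*

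**What the plan says.** The Protocol synopsis (section 2) gives the overall objective as to "demonstrate the safety and efficacy/performance of the ReUnion RFX System". It then names the means: "Safety of the ReUnion RFX System will be demonstrated through reporting of device-related intraoperative and postoperative Adverse Events (AEs".

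The endpoint text is softer. Protocol 8.3 introduces its secondary outcomes as things to be assessed and lists "Safety: Incidence of device-related intraoperative and postoperative AEs". Protocol 11.3.3 says: "The incidence of device-related AEs and implant survivorship will be assessed up to ten years after the index procedure and monitored through collection and analyses". Neither section, nor SAP 3.1.2, sets an acceptable rate, a comparator or a hypothesis for safety. Benchmarks, margins and power exist only for the ASES score (Protocol 8.1, 8.2 and 11.1; SAP 3.1.1 and 3.2).

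On the analysis, SAP 3.1 says that qualitative variables "will be analyzed listing the proportions, frequencies, column and row totals, and missing proportion (if any". In SAP Table 6.1.1 the row "Device-Related Adverse Event / Incident (Variable(s): AEEVENT; AEOTHER" is assigned "Proportions, frequencies, column and row totals, missing proportion (if any". The other tabulated AE rows, and the reoperation rows in Table 6.1.2, get the same treatment. The template in SAP 7.1 adds: "In addition to the number of frequencies, percentages must be displayed in a separate column". Its columns are n and %, by arm and in total. SAP 4.7 lists a confidence interval for the mean and none for a proportion.

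SAP Table 6.6.2 plans a Kaplan-Meier analysis of time to first device-related AE, for the final report. Its output includes the estimate, its standard error, cumulative events, remaining cases, and mean survival time with a 95% interval. SAP Table 6.7.3 plans the same for first reoperation.

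**The concern.** To demonstrate safety, a study needs either a result that would count against it or a statement of which event rates the data rule out. The synopsis offers neither, because the act of reporting is named as the demonstration. The tables that carry the endpoint show a percentage without its uncertainty.

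Protocol section 13 says the investigation serves European post-market requirements to support safety and performance, so the safety conclusion will be used. At stake is a report that says safety was demonstrated on the strength of a low or zero percentage, when the same data would be compatible with a noticeably higher true rate that no planned table shows.

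**Working it through.** **1. The plan's own figure.** Nothing in the documents sizes the study for safety. The only sizing figure is 80.3% power with 10 cases for ASES. It reproduces: effect (58.74 − 38.41)/20.33 = 1.0 for Arm A and (74.48 − 63.40)/11.08 = 1.0 for Arm B; a two-sided one-sample t-test at 0.05 with n = 10 has power 80.31%. It says nothing about AE rates.

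**2. Inputs for safety.** Total enrolment is 100 (Protocol 2 and 7). SAP section 6 splits all analyses by arm, and SAP 7.1 also asks for an overall result. No split between arms is given (Protocol 10.1 sets no assignment method), so any per-arm number is an assumption.

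**3. Zero events.** The exact (Clopper-Pearson) two-sided 95% upper limit with 0 of n is 1 − 0.025^(1/n). The one-sided 95% limit is 1 − 0.05^(1/n).

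| n | Source | Two-sided | One-sided |
|---|---|---|---|
| 100 | all subjects, both arms | 3.6% | 3.0% |
| 50 | one arm, even split assumed | 7.1% | 5.8% |
| 20 | a small arm (assumed); also the plan's target per indication | 16.8% | 13.9% |

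The chance of seeing no event at a true rate of 3% is 0.97^50 = 21.8% with 50 subjects and 0.97^100 = 4.8% with 100.

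**4. Some events.** Exact two-sided 95% intervals with 50 subjects:
- 1 event (2%): 0.1% to 10.6%
- 5 events (10%): 3.3% to 21.8%
- 10 events (20%): 10.0% to 33.7%

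The planned table would show only the 2%, 10% or 20%.

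**5. What the Kaplan-Meier output adds.** The usual (Greenwood) standard error is S(t) × √Σ[d/(r(r − d))], with d events among r at risk at each event time.
- No events: S = 1, the sum is empty, and the standard error is 0.
- One event in 50 with no censoring: S = 0.98 and the standard error is 0.98 × √(1/(50 × 49)) = 0.0198. This is informative, but the simple interval 0.98 ± 1.96 × 0.0198 runs from 0.941 to 1.019, past the possible maximum of 1.

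So the planned standard error helps once events occur. It shows no uncertainty when none do, which is when a claim of demonstrated safety is most tempting.

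**The case against.** The best defence is that safety is a secondary, descriptive endpoint in a post-market study of a device cleared before the study began. Protocol 8.3 and 11.3.3 already speak of assessing and monitoring, and section 5 of examining safety. On this view only the synopsis wording is loose. Safety oversight also has its own provisions: 48-hour reporting of serious events, sponsor review and yearly reports. Any reader can compute an exact interval from n and %. Much of this stands, and it keeps the point modest. It does not remove it: the synopsis states the study's objective, and its verb conflicts with the Protocol's own endpoint text. Table 6.1.1 counts event types and events per subject and site; it does not specify the proportion of subjects with at least one event.

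Four stronger readings are tempting, and the documents do not support them:
- *Any result would officially count as demonstrated safety.* This is an inference from one sentence and a missing criterion. No section says it.
- *No precision is planned for AEs.* The Kaplan-Meier standard error is planned in Tables 6.6.2 and 6.7.3.
- *The 56% drop-out leaves 50 × 0.44 = 22 per arm, hence an upper limit of 15.4%.* Protocol 9.3 keeps data collected up to withdrawal, loss, removal or death, and the Kaplan-Meier analysis censors at the last visit. Subjects who leave still contribute, so 22 is not the denominator for AE incidence.
- *The study is too small to exclude clinically relevant rates.* Neither document names such a rate, so this cannot be judged.

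**Conclusion.** The concern holds in a limited form. The synopsis promises a demonstration of safety, no criterion exists, and no interval is planned on any AE proportion or on the Kaplan-Meier estimate itself. With zero events the data would be compatible with true proportions up to 3.6% (100 subjects), 7.1% (50) or 16.8% (20), so *demonstrated* would not follow from the planned tables.

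The 50 and the 20 are assumed arm sizes, shown because the plan gives no split. All these limits treat each counted subject as fully observed for the period in question; with incomplete follow-up they would be wider. The ASES primary endpoint is not affected.

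**What to change.** 1. In the Protocol synopsis, replace *demonstrate* and *demonstrated*, where they refer to safety, with *estimate* or *describe*. This matches the endpoint text.
2. In SAP Table 6.1.1 add, per arm and overall, the number and proportion of subjects with at least one device-related AE, with an exact (Clopper-Pearson) 95% interval.
3. In SAP Tables 6.6.2 and 6.7.3 add pointwise 95% intervals for the Kaplan-Meier estimate at 24 months and 10 years, and state the method, since the simple form can exceed 1. If no event occurs, an interval built on the Greenwood standard error is uninformative, and the exact interval in item 2 should be used.

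The cost is a slightly weaker safety claim and a few extra table cells. No new data, visits or subjects are needed.

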## 4. Product Information

All components of the ReUnion RFX System have been cleared and approved for sale and use in the United States prior to starting the clinical investigation. 510(k) Clearance was received on 23Nov2016. This system is to be used only for indications for which it has been approved. Please see the approved Instructions for Use (IFU) and Operative Technique manuals for a detailed description of the medical device(s) and instrumentation as well as the intended use information.

Medical device product traceability will be achieved by capturing the implant lot number.

## 5. Risks and Benefits

This prospective, multicenter clinical investigation is designed to examine the safety and performance of the ReUnion RFX System in accordance with the approved IFU, labelling and instrumentation. The potential risks to subjects are described in the approved IFU and Operative Technique manuals.

Potential benefits resulting for the ReUnion RFX System over other devices and procedures as demonstrated by superior scoring on the outcome survey and positive results on other clinical evaluation measurements would suggest affirmative clinical efficacy.

## 6. Introduction

Proximal humerus fractures currently represent one of the most difficult surgical procedures in the upper extremity. Besides conservative treatment and open reduction and internal fixation (ORIF) with plates or intramedullary nails, shoulder arthroplasty represents an alternative treatment option for certain indications. Industry currently provides modular options allowing for easy, streamlined intraoperative decision making between anatomical hemiarthroplasty (HA), anatomical total shoulder arthroplasty (TSA) and reverse shoulder arthroplasty (RSA) as well as the option for later conversion or revision utilizing a prior well-fixed humeral stem.

The ReUnion RFX System is indicated for use as a HA, TSA or RSA. It includes a humeral fracture stem component which can be used in conjunction with the ReUnion TSA or ReUnion RSA humeral and glenoid components.

## 7. Clinical Investigation Design

This investigation is a prospective, multicenter clinical investigation. It is anticipated that a total of one hundred (100) subjects will be enrolled at approximately 5-10 sites. Neither subjects nor investigators are blinded to treatment and the clinical investigation does not include a contemporaneous control. The clinical investigation has been designed to follow the surgeon's standard of care for joint arthroplasty patients, which entails clinical evaluation on a regular ongoing basis, or as needed should the patient become symptomatic in the treated joint. The enrollment period is expected to occur over 20 months.

## 8. Objective

### 8.1. PRIMARY ENDPOINT – ARM A (TOTAL SHOULDER ARTHROPLASTY / HEMIARTHROPLASTY (TSA/HA))

**Degenerative, rheumatoid or post-traumatic arthritis of the shoulder joint and proximal humerus fractures:**

The primary objective of the clinical investigation is to demonstrate non-inferiority of the ASES Shoulder Score at 24 months postoperative compared to the benchmark literature for Arm A. The 24 months mean ASES Shoulder Score result of the RFX System (TSA/HA) will be compared to the pooled postoperative mean estimate of the control group (58.74 points). The pooled standard deviation of the postoperative ASES Shoulder Score result of the benchmark (20.33 points) was used to determine lower limit. The lower maximum acceptable difference ( $-\theta$ ) is 38.41 points (mean of control -  $\theta$  or  $58.74 - 20.33 = 38.41$  points).

Based on the underlying distribution of the data and the result of the normality assessment, either the parametric one-sample t-test or the non-parametric one-sample sign test will be used to compare the 24 months postoperative ASES Shoulder Score results of the ReUnion RFX System (TSA/HA) against the value of 38.41 points.

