#### 8.2. PRIMARY ENDPOINT – ARM B (REVERSE SHOULDER ARthroPLASTY (RSA))

##### **Degenerative, rheumatoid or post-traumatic arthritis, and gross rotator cuff deficiency of the shoulder joint and proximal humerus fractures:**

The primary objective of the clinical investigation is to demonstrate non-inferiority of the ASES Shoulder Score at 24 months postoperative compared to the benchmark literature for Arm B. The 24 months mean ASES Shoulder Score result of the RFX System (RSA) will be compared to the pooled postoperative mean estimate of the control group (74.48 points). The pooled standard deviation of the postoperative ASES Shoulder Score result of the benchmark (11.08 points) was used to determine the lower limit. The lower maximum acceptable difference ( $-\theta$ ) is 63.40 points (mean of control -  $\theta$  or  $74.48 - 11.08 = 63.40$  points).

Based on the underlying distribution of the data and the result of the normality assessment, either the parametric one-sample t-test or the non-parametric one-sample sign test will be used to compare the 24 months postoperative ASES Shoulder Score results of the ReUnion RFX System (RSA) against the value of 63.40 points.

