#### 11.1.2. Sample Size Justification - Arm B (RSA)

Benchmark and Objectives for Clinical Investigation					
Endpoint	Non-inferiority (equal or better) of the ASES Shoulder Score in relation to the officially cleared indications in comparison to respective clinical outcome data in the scientific literature.				
Meta-analysis by Shukla et al., 2016 [1]					
Benchmark Sources & Values ASES [points] for Arm B (RSA)					
Source	No.	Mean	Std. Dev.		
Source	Title	Mean	Std. Dev.		
1	Sebastia-Forcada, 2014 [3]	N/A	N/A		
2	Baudi, 2014 [4]	69.3	25.4		
3	Chalmers, 2014 [5]	80.0	11.0		
4	Cuff, 2013 [6]	77.0	3.75		
5	Garrigues, 2012 [7]	81.1	3.25		
6	Young, 2010 [8]	65.0	12.0		
7	Gallinet, 2009 [9]	N/A	N/A		
Identified Cleared Indications (Arm A & B)					
No.	Indication				
1	Aseptic necrosis of the humeral head				
2	Painful, disabling joint disease of the shoulder resulting from: degenerative arthritis, rheumatoid arthritis, or post-traumatic arthritis				
3	Proximal humeral fractures and/or dislocation				
4	Clinical management problems where arthrodesis or alternative reconstructive techniques are less likely to achieve satisfactory results				
5	Revision of previous unsuccessful total shoulder replacement, resurfacing or other procedure				
Explorative Analysis - ASES (single group) - for Arm B (RSA)					
Acceptance Criteria					

Confidence Interval (CI)	0.95 (95%) two-sided	
Software Used	IBM SPSS V20	
Descriptives		
Post-Op ASES Mean	Mean	74,4800 3,14124
	95% Confidence Interval for Mean	Lower Bound 65,7585 Upper Bound 83,2015
	Median	77,0000
	Std. Deviation	7,02403
	Minimum	65,00
	Maximum	81,10
	Interquartile Range	13,40
Post-Op ASES Std.Dev.	Mean	11,0800 4,00595
 
A box plot showing the distribution of Post-Op ASES Mean. The y-axis ranges from 60 to 85. The box represents the Interquartile Range (IQR) from approximately 68 to 78. The median is at 75. The whiskers extend from 65 to 81. A red horizontal line at 74.48 represents the Pooled mean ASES. Two blue horizontal lines at approximately 65.7585 and 83.2015 represent the 95% CI of the pooled mean ASES. A green horizontal line at 74.48 - 11.08 = 63.40 represents the Pooled mean ASES minus pooled std. dev. ASES.
		Red line: Pooled mean ASES Blue lines: 95% CI of pooled mean ASES Black line: Pooled median pooled ASES Box: Interquartile Range Green Line: Pooled mean ASES minus pooled std. dev. ASES $74.48 - 11.08 = 63.40$ points

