Confidence Interval (CI)	0.95 (95%)	
Tails	2	
Path	Non-inferiority – ReUnion RFX Arm A (TSA/HA) (A) ≥ Benchmark (B, explorative analysis in this document)	
Hypotheses Pair	Null (H ₀)	A – B < -θ
	Alternative (H ₁)	A – B ≥ -θ
Benchmark Timepoint	24 months postoperative	
Benchmark no. of sources	5	
Benchmark Mean	58.74 (pooled mean ASES [points])	
Benchmark Std. Dev.	20.33 (pooled std. dev. ASES [points])	
Benchmark Value Non-Inferiority Margin (-θ)	Pooled mean ASES minus pooled std. dev. ASES 58.74 – 20.33 = 38.41 points	
Software Used	IBM SPSS Sample Power V3.0	
IBM SPSS Sample Power Output		

One goal of the proposed clinical investigation is to test the null hypothesis that the population mean is 58.74 points. The criterion for significance (alpha) has been set at 0.05. The test is 2-tailed, which means that effects in both directions will be interpreted. With the proposed sample size of 10 cases, the clinical investigation will have power of 80.3% to yield a statistically significant result. This computation assumes that the population from which the sample will be drawn has a mean of 58.74 points with a standard deviation of 20.33 points. The observed value will be tested against a theoretical value (constant, non-inferiority margin) of 38.41 points.
		
IBM SPSS Sample Power Output – Screenshot		

Estimated overall drop-out rate is 56% which leads to the requirement of enrolling an additional 6 subjects into the clinical investigation.
		
Sample Size	Overall number of subjects to be enrolled: 16 subjects (rounded up to 20 subjects)	
Overall Sample Size (multiplied by number of indications = 5)	100 subjects	

Table 3.2.1: Sample Size Justification Arm A (TSA/HA)

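### Each non-inferiority margin is one between-patient SD with no justification, so a passing arm, chiefly Arm A, can lie wholly below the benchmark yet be reported as at least equal to it

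*Protocol*

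**What the plan says.** Protocol 8.1 (Arm A) and 8.2 (Arm B) build each pass mark as the benchmark mean minus the benchmark SD.

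- **Arm A:** "The pooled standard deviation of the postoperative ASES Shoulder Score result of the benchmark (20.33 points) was used to determine lower limit", giving 58.74 − 20.33 = 38.41. The 24-month scores are tested "against the value of 38.41 points".
- **Arm B:** "The pooled standard deviation of the postoperative ASES Shoulder Score result of the benchmark (11.08 points) was used to determine the lower limit", giving 74.48 − 11.08 = 63.40.

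Protocol 11.3.2 and SAP 3.1.1, 3.2 and 6.6 repeat these figures. The only rationale is in Protocol 11.3.2 and SAP 3.1.1: some lower limit is needed because sample estimates vary. Nothing explains why it should be one SD.

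The benchmark tables (Protocol 11.1.1 and 11.1.2; SAP 3.2.1 and 3.2.2) also print the spread of the series means. For Arm A the minimum is 47.40 and the 95% CI for the mean is 47.71 to 69.77. For Arm B the minimum is 65.00 and the CI is printed as "Lower Bound 65,7585 Upper Bound 83,2015".

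The hypothesis tables (Protocol Tables 3a and 4a; SAP Tables 3.1.1.1 and 3.1.1.2) translate p ≤ 0.05 into RFX ≥ Control. The surrounding text describes success as a result that matches or exceeds the control.

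**The concern.** A between-patient SD describes how far patients differ from one another. It does not say how much loss in the mean is tolerable, nor how precisely the benchmark mean is known. Used as a margin, it makes the test easier when the literature is noisier. On the same 0–100 type of score, Arm A may lose 20.33 points (20.33/58.74 = 35% of its benchmark) and Arm B 11.08 points (11.08/74.48 = 15%), only because the Arm A series are more variable.

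A margin equal to the planning SD also fixes the standardised effect at 1.0. That is why two arms with different benchmarks both show n = 10 and 80.3% power. The sample size reflects no chosen difference.

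What is at stake is the primary conclusion. The test shows only that the mean exceeds 38.41 or 63.40, while the decision table calls this at least equal to the control. A report could print that conclusion beside a 95% CI that excludes the benchmark from below.

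**Working it through.** **Inputs.** Means, SDs and series values come from Protocol 11.1.1 and 11.1.2. The one-sided 5% test comes from 11.3.2. The benchmark is treated as a constant, as the plan does.

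**1. Reproduce the plan's figures.**
- Arm A: the unweighted mean of 51.3, 66.0, 62.0, 47.4 and 67.0 is 58.74, SE 3.972, lower 95% limit 47.71. The mean of the five SDs is 20.33.
- Arm B: the mean is 74.48, SE 3.141, lower limit 65.76. The mean of the five SDs is 11.08.
- The SDs are plain averages. The root-mean-square values would be 21.48 and 13.67.
- Power: one-sample t-test, effect 1.0 SD, n = 10, two-sided 0.05 gives 0.803, matching 80.3%. The one-sided test that will be used has 0.898.

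**2. Place the pass marks against the benchmark.**
- Arm A: 47.40 − 38.41 = 8.99 below the lowest series; 47.71 − 38.41 = 9.30 below the CI limit.
- Arm B: 65.00 − 63.40 = 1.60 below the lowest series; 65.76 − 63.40 = 2.36 below the CI limit.

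**3. Can an arm pass while its two-sided 95% CI is wholly below the benchmark?**
- Lowest passing mean = pass mark + t(0.95, n−1) × SD/√n.
- Highest mean with the CI wholly below = benchmark − t(0.975, n−1) × SD/√n.
- Overlap exists when the first is lower than the second.

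| n per arm | A: passes from | A: CI below up to | B: passes from | B: CI below up to |
|---|---|---|---|---|
| 10 | 50.19 | 44.20 | 69.82 | 66.55 |
| 15 | 47.66 | 47.48 | 68.44 | 68.34 |
| 16 | 47.32 | 47.91 | 68.26 | 68.58 |
| 22 | 45.87 | 49.73 | 67.46 | 69.57 |
| 50 | 43.23 | 52.96 | 66.03 | 71.33 |

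Overlap starts at 16 evaluable subjects. At n = 10 it needs an observed SD below √10/(1.833 + 2.262) = 0.77 of the planning SD.

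The row n = 22 assumes an even split of the 100 subjects and 56% loss: 50 × 0.44 = 22. For Arm A, SE = 20.33/√22 = 4.334, the lowest passing mean is 38.41 + 1.721 × 4.334 = 45.87, and its CI is 45.87 ± 2.080 × 4.334 = 36.9 to 54.9, below 58.74. For Arm B the same steps give 67.46 and 62.6 to 72.4, below 74.48. The row n = 50 assumes an even split and no loss.

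**4. Chance of passing when the true mean equals the worst series.** Noncentral t, ncp = (true mean − pass mark)/SD × √n, one-sided 5%.

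| n | A at 47.4 | B at 65.0 |
|---|---|---|
| 10 | 36% | 11% |
| 22 | 64% | 16% |
| 50 | 92% | 26% |

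**5. True mean half an SD below the benchmark (A 48.58, B 68.94).** Either arm passes 73% of the time at n = 22 and 97% at n = 50. By simulation it passes and is also significantly below the benchmark in about 35% and 90% of trials, and in about 3% at n = 10.

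**6. Power against the printed lower limits, 47.71 and 65.76.** With the true mean at the benchmark and a one-sided 5% test: 48% (A) and 74% (B) at n = 10; 79% and 97% at n = 22.

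**The case against.** Four points on the other side have substance.

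**Arm B separates good from poor.** A reader might infer that the primary test cannot tell a device that performs like the literature from one worse than all of it. For Arm B the figures do not support that. The lower bound, not the mean, must clear 63.40, so the lowest passing mean stays above 65.0 until n is about 132, more than the whole study. A device at 65.0 passes 11–26% of the time; one at the benchmark passes 90% at n = 10 and over 99% at n = 22. This stands.

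**The overlap is conditional.** A reader might also infer that a significantly worse arm can pass at any sample size. At the planning SD it needs about 16 evaluable subjects, and at the powered n = 10 it is rare. The documents give no split by arm, and the 56% loss is cited to a follow-up report of at least 10 years, so neither is established for 24 months. Allowing for the benchmark's own SE (Welch, five series), an arm at the passing limit still differs in Arm A (p = 0.045 at n = 22; 0.011 at n = 50), but less clearly in Arm B (0.11; 0.051). This stands too.

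**The printed CI limits are not self-evidently the right margin.** They also loosen when studies are few or discordant, and they do not measure acceptable loss. The documents do not support treating 47.71 and 65.76 as the only correct limits.

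**The CI is already tabulated.** SAP Table 6.5.2 requires the mean and 95% CI of the total score at each visit, so an alert reader could see the conflict. That helps transparency but leaves the conclusion rule unchanged.

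**Conclusion.** The concern holds, chiefly for Arm A. Both margins rest on a quantity unrelated to acceptable loss, and both pass marks lie below all the benchmark evidence at any sample size. The stated conclusion claims more than the test can show.

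The possibility of passing with a CI wholly below the benchmark is real in both arms from about 16 evaluable subjects, at the planning SD and with the benchmark taken as fixed. An even split of 100 subjects would exceed that number even after 56% loss, but that split is an assumption. The failure to screen out a device at the level of the worst series is an Arm A problem (36–92% pass) and not an Arm B one (11–26%).

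**What to change.** 1. **Conclusion wording.** In Protocol 11.3.2 (Tables 3a and 4a) and SAP 3.1.1, replace RFX ≥ Control, and the accompanying description of success as matching or exceeding the control, with what the test shows: the mean exceeds 38.41 (A) or 63.40 (B), that is, it is not worse than the benchmark by more than 20.33 or 11.08 points.
2. **Supportive comparison.** In SAP 6.6, pre-specify that each arm's 95% CI is reported against 58.74 or 74.48, and that the report says so when the CI lies wholly below. Also pre-specify that the one-sided 95% lower bound is compared, as a supportive criterion, with a stricter limit such as the printed 47.71 or 65.76.
3. **Margin.** In Protocol 8.1 and 8.2, justify one SD or replace it with a justified margin. The printed limits are one option among several.

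**Cost.** Steps 1 and 2 need wording and one extra comparison per arm, with data already collected and no added patients. The claim becomes weaker, and the stricter comparison has limited power if few subjects are evaluable (48% and 74% at n = 10). If step 3 changes the primary margin, Protocol 11.1 and SAP 3.2 must be recalculated. With the printed limits, 80% power needs 23 (A) and 12 (B) evaluable one-sided, or 29 and 15 two-sided. Because the study is open-label with yearly reports, the changes should be fixed before the 24-month data are reviewed.
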